## 5.0 Inclusion and Exclusion Criteria/Study Population

Admission into the study is open to men and women, ages 25 to 65, and to all racial and ethnic groups. Based on the published R21 report (on which this study is based), we anticipate we will screen (by telephone or in person) approximately 316 potential participants. A brief phone screening will assess participant suitability via inclusion/exclusion criteria. Qualifying individuals will be scheduled to undergo (i) informed consent, (ii) demographic information collection, and (iii)

**Fig. 4: Amygdala-cortico-striatal rsFC:** rsFC was assessed in smokers ( $N=18$ ) while sated and following 24hrs smoking abstinence. Compared to sated, the effects of abstinence on rsFC were examined using whole brain analyses. Abstinence strengthened rsFC connectivity between the amygdala, striatum and mPFC ( $p<.05$ ).

comprehensive clinical assessment of smoking behavior/nicotine dependence, general psychiatric functioning, and substance use. The instruments employed in this assessment are the same as those used in the R21; they are widely cited and have strong psychometric properties. Assessments include the: a) Smoking History Form^99, a 20-item interview that solicits detailed information about smoking history, including initiation and duration; b) Fagerström Test for Nicotine Dependence (FTND), a brief measure of nicotine dependence; c) Wisconsin Inventory of Smoking Dependence Motives (WISDM-68), a multidimensional assessment of nicotine dependence; d) Contemplation Ladder to measure readiness to quit; e) Wisconsin Predicting Patients' Relapse questionnaire (WPPR^103) which assesses relapse potential and may serve as covariate in the analysis; f) Michigan Nicotine Reinforcement Questionnaire (MNRQ) which assesses both positive and negative reinforcement from smoking; g) Beck Depression Inventory (BDI); and h) the Mini-International Neuropsychiatric Interview or MINI which assesses general psychiatric functioning and other alcohol/substance dependence (per inclusion/exclusion criteria). Quantity and frequency assessment of smoking and other substance use in the three months prior to study involvement will be assessed using the Timeline Follow-Back (TLFB).

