fMRI sample size estimation. Though we have not assessed the effects of RET on fMRI BOLD response, the four human fear conditioning studies of RET described above reported significant BOLD and connectivity changes with n's ranging from 19 to 23. Additionally, some of our previous work provides strong support that we will observe significant effects with group n's in this range. In two prior fMRI CR studies of smoking/smoking abstinence (n's=17-19), effects sizes for CR-BOLD response ranged between  $d=.65$  to 1.5. In two prior rsFC studies in cigarette smokers (n's 16-18), we found smoking abstinence, compared to satiety, strengthened rsFC in an amygdala-striatal circuit ( $rZ$ 's between .56 and .91); whereas in Froeliger et al 2015 the strength of rsFC in the frontostriatal pathway was associated with less craving ( $R^2=.48$ ) and smoking (CO confirmed:  $R^2=.50$ ). In the proposed study, we will examine the effects of RET on drug CR-BOLD response (Hypothesis 2a) and rsFC (Hypothesis 2b). If we assume, based on our prior work and that of others, that these effects are of medium to large size (e.g.  $D \approx .8$ ), then with a full fMRI sample of N=68 (34 per group) and  $\alpha =.05$  (1-tailed), a final sample of  $\approx 23$  participants in each group (accounting for fMRI ineligibility and 30% attrition) will result in power  $>.80$  for detecting effects on CR-BOLD response and rsFC.

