sequence (36 slices, TR = 2200 ms, TE = 35 ms, FOV =192, matrix = 64x64, 3mm^3 voxels). The participant's head will be immobilized. Prior to the acquisition of images, the anterior (AC) and posterior commissures (PC) will be identified in the mid-sagittal slice of a localizer series. High-resolution anatomical imaging. A high-resolution 3D MPRAGE anatomical sequence will be acquired (matrix = 256, flip angle = 9°, 166 slices, slice thickness = 1 mm). Following preprocessing procedure and 1st level modeling as described in each respective specific aim, 2nd level modeling will be conducted within the confines of an ROI mask acquired from the Wake Forest University Pickatlas and drawn on the MNI template. This ROI approach reduces Type I error by restricting analyses to a smaller set of voxels. Follow-up voxel-wise exploratory analyses will be conducted (p>.05, FWE).

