Validity and data integrity will be checked on an ongoing basis through the use of data audits. Study statisticians ([name]/[name]) will supervise quarterly data quality assessments (i.e., examination of the outcomes database(s) for missing data, unexpected distributions or responses, and outliers) performed by the study research staff. Accuracy and completeness of the data collected will be ensured by weekly review. A 10% random sample of the primary source document will be crosschecked with the database on a quarterly basis. If inaccuracies exceed 2%, then a second 10% will be randomly chosen for audit. Should data discrepancies be discovered, they will be resolved using original source documents. The REDCap system does not accept outliers, illogical response patterns, etc. The PI will have weekly meetings with the research staff to discuss qualitative comments received during data collection and any problems in data collection or entry. The statistician will periodically examine the database to look for irregularities. Initial data analyses will examine distributions of variable scores and comparability of baseline characteristics across conditions in case analyses need to be adjusted for these.

**fMRI Analysis Plan.** The hypothesis for 2a (CR) is that Group R-E will evidence attenuated CR in medial prefrontal cortex (mPFC: dorsal anterior cingulate-dACC; ventromedial: vmPFC), limbic regions (amygdala, hippocampus) and ventral striatum. Greater reduction in BOLD response in regions of interest will predict decreased smoking. fMRI data will be preprocessed using recommended procedures in SPM8 and as done previously. At the 1st-level, data will be analyzed using the GLM; events of interest (Smoking, Neutral) will be modeled as a boxcar canonically convolved hemodynamic response function, and HR and motion parameters entered as nuisance covariates. At the 2nd-level, 2 (Time: Pre, Post) x 2 (Group: R-E, NR-E) ANOVA will be used within an *a priori* ROI mask (amygdala, hippocampus, mPFC, ventral striatum;  $p < .05$ , pFWE). **Hypothesis for 2b (rsFC)** is that group R-E will evidence strengthened rsFC in frontostriatal circuitry; weakened rsFC in frontolimbic circuitry and the magnitude of rsFC will be inversely related to craving and smoking (e.g., CPD). **fMRI data analysis plan.** Similar to our previous work along with in scanner heart-rate and respiration entered as covariates, rsFC will

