be assessed using the conn13 SPM8 toolbox. Connectivity matrix for each seed (see ROI mask in 2a) will be entered into separate: 2 (Time: Pre, Post) x 2 (Group) ANOVA. Exploratory voxel-wise analyses are planned for 2a and 2b with specific focus on subdivisions of the insular cortex (cf., Addicott et. al., 2015).

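### The only threshold stated for the exploratory voxel-wise fMRI analyses has its inequality reversed (p>.05 instead of p<.05, FWE)

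*Combined protocol and SAP*

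**What the plan says.** Three places in the combined protocol and SAP bear on this point.

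- **Section 10.0, item vi (General Neuroimaging Methods).** Second-level modelling is confined to a region-of-interest (ROI) mask, for this reason: "This ROI approach reduces Type I error by restricting analyses to a smaller set of voxels". The next sentence gives the rule for analyses outside that restriction: "Follow-up voxel-wise exploratory analyses will be conducted (p>.05, FWE".
- **Section 12.0, fMRI Analysis Plan, hypothesis 2a.** The Time by Group ANOVA is run within an a priori "ROI mask (amygdala, hippocampus, mPFC, ventral striatum", and the threshold attached to that mask is p < .05, pFWE.
- **Section 12.0, fMRI Analysis Plan, end of hypothesis 2b.** The plan adds: "Exploratory voxel-wise analyses are planned for 2a and 2b with specific focus on subdivisions of the insular cortex". No threshold accompanies this sentence.

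**The concern.** The rule in section 10.0, item vi, decides which voxels are declared significant, and its inequality points the opposite way from the ROI rule in section 12.0. It stands in current methods text, not in background or a history of changes. Section 12.0 supplies no threshold of its own for the exploratory voxel-wise work, so there is no correct statement elsewhere to override the wrong one.

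Taken literally, the plan would report voxels that do not survive family-wise correction. More realistically, whoever runs the exploratory and insula analyses must infer the criterion. Choice of threshold is one of the main freedoms in voxel-wise imaging analysis, so it should be fixed in writing beforehand.

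**Working it through.** The disputed item is the direction of an inequality, so the plan has no figure to reproduce. The check sets the stated rules side by side, works out what each direction means, and confirms that nothing else depends on the sign.

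**1. The stated thresholds**

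| Analysis | Place | Threshold |
|---|---|---|
| ROI-mask ANOVA, hypothesis 2a | 12.0, fMRI Analysis Plan | p < .05, pFWE |
| Follow-up voxel-wise exploratory | 10.0, item vi | p > .05, FWE |
| Exploratory voxel-wise for 2a and 2b, insula focus | 12.0, end of fMRI Analysis Plan | none |
| Preliminary whole-brain connectivity data | Fig. 4 caption, in section 5.0 | p < .05 |

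Both other rows that state a threshold use the less-than sign. The sentence just before the printed rule gives control of Type I error as the reason for the ROI approach, and a rule that keeps non-significant voxels contradicts that purpose.

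**2. What each direction does**

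Suppose there is no effect at any voxel, and take the smallest family-wise-corrected p-value in the search volume as uniform on (0, 1).

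- Rule p < .05: P(at least one voxel declared) = 0.05. This is the error rate that FWE correction is meant to deliver.
- Rule p > .05: P(every voxel meets the rule) = 1 − 0.05 = 0.95.

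The printed rule therefore selects the complement of the significant set and cannot serve as a significance criterion.

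**3. Whether another statement covers the insula analyses**

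The p < .05, pFWE rule in section 12.0 is tied to a mask of amygdala, hippocampus, mPFC and ventral striatum. The insula is not in it, so that rule does not extend to the insula analyses. Two readings remain:

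- If the exploratory analyses in sections 10.0 and 12.0 are the same, their only stated criterion is the reversed one.
- If they are different, those in section 12.0 have no stated criterion.

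Either way, the insula analyses lack a correctly stated threshold.

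**4. Whether any design figure depends on the sign**

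The fMRI sample-size paragraph in section 10.0, item iii, assumes d ≈ 0.8, about 23 per group after attrition, and a one-tailed alpha of .05.

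- Attrition: 34 × 0.70 = 23.8, consistent with about 23.
- Power, normal approximation: 0.8 × √(23/2) − 1.645 = 2.713 − 1.645 = 1.068, and Φ(1.068) = 0.857.
- Power, noncentral t with 44 degrees of freedom: 0.848.

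Both agree with the plan's claim of power above .80. The voxel-wise threshold does not enter this calculation, so correcting it changes nothing here.

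**The case against.** The strongest reply is that this is a proofreading matter. The level (.05) and the type of correction (FWE) are both stated, and only one character is wrong. The neighbouring sentence, the ROI rule and the Fig. 4 caption make the intention clear, and no competent analyst would report voxels because they failed correction. The analyses are labelled exploratory in both sections, and no confirmatory hypothesis relies on them. If the general methods threshold already governs all voxel-wise work, repeating it in section 12.0 is a matter of editorial taste.

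Most of this stands, and it limits the importance of the point. It does not make the text correct. The intended threshold has to be inferred, because no sentence states it correctly for these analyses. The plan also does not say that the analyses in the two sections are the same, which is a reason to state the threshold in section 12.0.

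A second reply is that the sign may have been misread when the text was extracted from PDF. That cannot be excluded entirely. However, the less-than sign comes through correctly elsewhere, including in ordinary text under Inclusion of Children, and the character here is a clean greater-than sign. A look at the source file would settle it. If the source is correct, the remaining gap is the missing threshold in section 12.0.

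**Conclusion.** The concern holds. The threshold for the exploratory voxel-wise analyses is wrong as written: it reverses the direction used for the ROI analysis, and no correct threshold for the exploratory or insula analyses appears elsewhere in the plan.

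The point is minor. It bears on the exploratory whole-brain and insula results only. The primary CPD analysis, the craving analysis and the ROI test for hypothesis 2a are unaffected, and no sample size or power figure moves. The conclusion assumes that the extracted text matches the source document, and that p < .05 with FWE correction was intended. The plan's own ROI rule and its stated aim of limiting Type I error support the second assumption.

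**What to change.** In section 10.0, item vi, change the rule for the follow-up voxel-wise analyses to p < .05, FWE-corrected. In section 12.0, at the sentence introducing the exploratory voxel-wise analyses for 2a and 2b, add the same threshold and say that it is the rule from section 10.0, item vi.

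The cost is one character and one added phrase. Design, data collection, sample size and participant procedures do not change.

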**Procedures: Items viii thru xi below describe major procedural elements in the study (cf., Fig. 6 above).**

**vii. Clinical Assessment and Randomization:** A brief phone screening will assess participant suitability via inclusion/exclusion criteria. Qualifying individuals will be scheduled to undergo (i) informed consent, (ii) demographic information collection, and (iii) comprehensive clinical assessment of smoking behavior/nicotine dependence, general psychiatric functioning, and substance use. The instruments employed in this assessment are the same as those used in the R21; they are widely cited and have strong psychometric properties. Assessments include the: a) Smoking History Form^99, a 20-item interview that solicits detailed information about smoking history, including initiation and duration; b) Fagerström Test for Nicotine Dependence (FTND), a brief measure of nicotine dependence; c) Wisconsin Inventory of Smoking Dependence Motives (WISDM-68), a multidimensional assessment of nicotine dependence; d) Contemplation Ladder to measure readiness to quit; e) Wisconsin Predicting Patients' Relapse questionnaire (WPPR^103) which assesses relapse potential and may serve as covariate in the analysis; f) Michigan Nicotine Reinforcement Questionnaire (MNRQ) which assesses both positive and negative reinforcement from smoking; g) Beck Depression Inventory (BDI); and h) the Mini-International Neuropsychiatric Interview or MINI which assesses general psychiatric functioning and other alcohol/substance dependence (per inclusion/exclusion criteria). Quantity and frequency assessment of smoking and other substance use in the three months prior to study involvement will be assessed using the Timeline Follow-Back (TLFB). At the conclusion of the assessment, a saliva sample will also be collected to establish baseline cotinine levels; next, participants will be scheduled for their baseline cue reactivity assessment and fMRI session. They will be informed that they will be (1) required to be abstinent from alcohol and other drugs on the day of the session, and (2) compensated to remain abstinent from smoking starting at bedtime the night before their appointment. Overnight smoking/substance abstinence prior to baseline session is necessary so that responses are collected under the same conditions of compensated abstinence as those that will be in force during the intervention and initial 24-hr. post-treatment cue reactivity/fMRI test session.

Lastly, study staff will randomize participants to treatment group and fMRI condition. Participants will be randomized to the Group R-E or NR-E in a 1:1 allocation. Randomization will be done using a stratified random block design; randomization blocks will vary in size (3, 6 and 9) and randomization will be stratified across gender and baseline nicotine dependency (FTND score ≤ 5 vs. > 5). Relevant data from the clinical assessment will be used to assign participants to the corresponding randomization strata; then randomized within the current block of the strata. Following treatment randomization, participants will be randomized to receive fMRI or no fMRI in a 1:1 allocation (within each treatment strata) until 34 participants in each treatment assignment (68 total) have been successfully randomized to the fMRI protocol. This approach to randomization should mitigate accidental bias and produce comparable groups across possible confounds.

**viii. Baseline Cue Reactivity/fMRI Assessment:** The baseline CR session will be administered at one of our two identical lab locations (ABRL or TRAIN). Upon arrival, participants will undergo a smoking abstinence assessment involving self-report verification followed by breath CO assessment. Per recent study guidelines, participants will be considered overnight abstinent if their breath CO level is ≤ 10 ppm. Abstinence from alcohol/other drug use will be

assessed via breathalyzer and urine drug screen (UDS). Failure to meet abstinence requirements will result in rescheduling. Following the abstinence assessment, participants will be seated comfortably in front of a computer monitor and have the HR and SC sensors and BP cuff affixed as described above. They will remain seated comfortably for 10 min, after which 50-sec of continuous HR and SC data will be collected; next the participant will complete the CQ, MF and have their BP assessed. Having completed pre-cue assessments, the participant will remain seated for 5-min; they will then view the smoking-related video described above. Continuous HR and SC will be collected during the first 50-sec of the video whereas the CQ, MF and BP will be collected immediately after viewing the video. Following a break, participants randomized to the fMRI condition will be escorted to the fMRI suite. Participants will practice the experimental task while inside a mock scanner in order to reduce scan-related anxiety and enhance data integrity. Next, participants will be administered the fMRI procedures. In brief, we will collect a hi-res MPRAGE structural image, followed by 6-minute eyes-closed resting-state sequence and then participants will be scanned while performing a smoking CR task (8 ½ min duration) that involves viewing alternating blocks of neutral cues (e.g. pencil: 40 sec), fixation and craving ratings (30 sec) and smoking cues (e.g. cigarette: 40 sec). Participants not randomized to the fMRI condition will remain in the CR laboratory and receive the same CR regimen as administered in the fMRI condition. This ensures that all participants have equivalent stimulus exposure.

At the completion of the baseline CR/fMRI assessment, participants will schedule their next visit with study staff, and they will be reminded that their quit attempt will begin the night before and that it will be the first of four consecutive daily visits for which they will receive abstinence-based compensation. The rationale for implementing a reinforced abstinence procedure was to ensure that extra-study smoking (e.g., at home) does not interfere with any effects of treatment (RET or otherwise) or the treatment effects assessed in the initial 24-hr test session. Lastly, participants will receive compensation.

**ix. Intervention:** Three intervention sessions will be performed on consecutive days. Participants will arrive at the ABRL/TRAIN lab and compliance with abstinence (breath CO, UDS and breathalyzer) will be assessed. If the participant fails the abstinence assessment, they will be rescheduled; however, if the participant fails the abstinence assessment on the second/third day, they will be permitted to continue in the protocol. This is a departure from the R21, where participants violating the abstinence assessment were discharged from the study. Importantly, the compensation schedule we used to reinforce abstinence resulted in only 10% of the sample being discontinued during treatment. In the present study, we have elected to retain these individuals in the interest of being able to conduct a full intent-to-treat analysis, which we believe is a strength. To discourage multiple violations of abstinence, participants will lose their compensation on the day of the violation but will have the ability to re-earn it by remaining abstinent for the remaining treatment session(s) and the 24-hour test session. Following the abstinence assessment, use of any nicotine products (e.g., e-cigarettes, dip, gum, patch) during the prior 24-hr. period will be assessed. Next, pre-cue measures of craving and physiological reactivity will be obtained as described above for the baseline assessment. After pre-cue measures, individuals in Group R-E will watch the 5-min. video with smoking-related content (same as viewed during baseline cue reactivity) whereas individuals in Group NR-E will view the 5-min. control video with neutral, smoking-irrelevant content. Continuous HR and SC will be collected during the video and the remaining assessments (CQ, MF and BP) will be obtained after. Participants in all three groups will remain seated for 10-min and then Groups R-E and NR-E will be administered a 1-hr of extinction training. As noted above, this 1-hr. training will consist of four sequences of video, picture and in vivo cue exposure. Continuous HR and SC will be collected during the first cue format presented in each sequence and the CQ, MF and BP will be obtained immediately following the last cue format of each sequence (i.e., during a 2-min period where no stimuli are presented). At the completion of exposure training, participants will be asked to sit comfortably for 5-min while the study coordinator removes the HR/SC sensors and the BP cuff. Participants will be reminded that they are being compensated to remain abstinent from smoking and other substance use during the remaining intervention session(s) and/or the 24-hr. test session.

**x. Test Sessions:** Participants will complete seven follow-up test sessions: 24-hours, 2-weeks and 1-month, 6-weeks, 2-, 3- and 6-months. We use monetary compensation to minimize test session attrition (only 17.2% of participants did not complete the R21). Consistent with the R21 and Xue et al., 2012, each test sessions will involve a CR assessment identical to the baseline CR assessment described above except that a brief novel smoking picture cue sequence will also be presented. Importantly, some procedural elements will not occur in all test sessions. First, only the 24-hour follow-up test session will be performed under conditions of reinforced abstinence. The goal will be to assess the acute effects of the interventions under the same conditions of abstinence that occurred during the intervention. Participants will be encouraged to maintain their smoking abstinence at the conclusion of this session but will not be compensated for it (participants will be given a referral to the SC state Quitline, a free, anonymous service that supports abstinence). Second, for individuals randomized to the fMRI condition, the 24-hr test session is the only one in which an fMRI session (identical to the one in the baseline assessment) will be performed immediately after the initial CR assessment (cf., Fig. 6); those not assigned to the fMRI condition will remain in the CR laboratory and receive the same CR regimen as administered in the fMRI condition. Third, at the end of all but the 6-mo. test session, participants will receive a smoking diary in which to record the occurrence of both daily smoking and craving. A TLFB assessment of smoking behavior will be performed whenever diary data is not available; all but one of the R21 participants used their diary to collect smoking data as instructed. For those follow-up periods where more than 2-weeks elapse between visits (i.e., period between the 2 and 3 mo. follow-up visit and the period between the 3 and 6 mo. visit), study staff will phone contact participants every 2 weeks to collect diary data. Fourth, in all but the 24-hr. follow-up test session, expired CO and a saliva sample will be collected in order to biochemically corroborate, via CO and cotinine levels, self-report smoking/abstinence (salivary cotinine abstinence cutoff  $\leq$  15 ng/ml per SRNT Guidelines and CO abstinence cutoff  $\leq$  5 ppm). Assessment of the use of any nicotine products (e.g., e-cigarettes, dip, gum, patch) will be assessed at all follow-up visits. At study completion, debriefing will occur in which participant questions will be addressed and recommendations for additional cessation treatment will be provided.

**xii. Participant Compensation:** Study retention will be promoted by the following compensation schedule: Clinical assessment = \$30.00; Baseline cue reactivity/fMRI = \$60.00; Intervention sessions 1, 2 & 3 = \$75.00, \$100.00 and \$125.00, respectively; 24-hr. follow-up test session 1 = \$150.00; Test sessions at 2-wks, 1-mo., 6-wks, 2-mo., 3-mo., & 6-mo. = \$100.00. Maximum compensation for participation is \$1,140.00. Retention will also be fostered by frequent phone/text contacts between study staff and participants.

